12.7.10 Laboratory tests

Output name	Display*	Title (Description)	Analysis set(s)**	Key deliverable	Mock layout
LB_SUM_HEM	T	Summary and change from baseline of hematology values, by visit	SAF ivSAF#		T_LB_SUM
LB_SUM_CHE	T	Summary and change from baseline of biochemistry values, by visit	SAF ivSAF#		T_LB_SUM
LB_ABN_P2	T	Incidence of marked laboratory values, by period	SAF ivSAF#		T_LB_ABN

* T=Summary table, L=Listing, F=Figure, **SCR=Screened analysis set, SAF=Safety analysis set, ivSAF=i.v. Safety analysis set, PKS=Pharmacokinetic analysis set, # Tables will run on SAF only if SAF and ivSAF are identical.

12.7.11 Vital signs and body weight

Output name	Display*	Title (Description)	Analysis set(s)**	Key deliverable	Mock layout
VS_WGT_SUM	T	Summary and change from baseline of body weight, by visit	SAF ivSAF#		T_LB_SUM
VS_SUM	T	Summary and change from baseline of vital signs, by visit	SAF ivSAF#		T_VS_SUM
VS_PRED_S	T	Summary of post-dose values and change from pre-dose of vital signs, by visit	SAF ivSAF#	Y	T_VS_PREADS
VS_ABN	T	Incidence of marked blood pressure abnormalities, by period	SAF ivSAF#	Y	T_VS_ABN

* T=Summary table, L=Listing, F=Figure, **SCR=Screened analysis set, SAF=Safety analysis set, ivSAF=i.v. Safety analysis set, PKS=Pharmacokinetic analysis set, # Tables will run on SAF only if SAF and ivSAF are identical.

12.7.12ECG

Output name	Display*	Title (Description)	Analysis set(s)**	Key deliverable	Mock layout
EG_SUM	T	Summary and change from baseline of quantitative ECG parameters, by visit	SAF ivSAF#		T_EG_SUM
EG_PRED	T	Summary of post-dose values and change from pre-dose of quantitative ECG parameters, by visit	SAF ivSAF#		T_EG_PRES
EG_QUAL_SUM	T	Summary of qualitative ECG findings, by visit	SAF ivSAF#		T_EG_QUAL
EG_ABN	T	Incidence of ECG abnormalities - QT prolongation, by period	SAF ivSAF#		T_EG_AB

* T=Summary table, L=Listing, F=Figure, **SCR=Screened analysis set, SAF=Safety analysis set, ivSAF=i.v. Safety analysis set, PKS=Pharmacokinetic analysis set, # Tables will run on SAF only if SAF and ivSAF are identical.

12.7.13WHO Functional class

Output name	Display*	Title (Description)	Analysis set(s)**	Key deliverable	Mock layout
WHO_SUM	T	Summary of WHO functional class, by visit [include a best/worst post baseline category]	SAF ivSAF#		T_WHO_SUM
WHO_CHG	T	Shift table of WHO functional class from baseline to each study visit [include a shift to worst/best post baseline category]	SAF ivSAF#		T_WHO_CHG

* T=Summary table, L=Listing, F=Figure, **SCR=Screened analysis set, SAF=Safety analysis set, ivSAF=i.v. Safety analysis set, PKS=Pharmacokinetic analysis set, # Tables will run on SAF only if SAF and ivSAF are identical.

12.8 PK analyses

Output name	Display*	Title (Description)	Analysis set(s)**	Key deliverable	Mock layout
PK_CON_SUM_SEL	T	Summary of selexipag plasma concentrations [ng/mL] per time point by dose level and treatment	PKS		T_PK_CON_SUM

Output name	Display*	Title (Description)	Analysis set(s)**	Key deliverable	Mock layout
PK_CON_SUM_ACT	T	Summary of ACT-333679 plasma concentrations [ng/mL] per time point by dose level and treatment	PKS		T_PK_CON_SUM
PK_EP_SUM_SEL	T	Summary of PK endpoints of selexipag by dose level and treatment	PKS	Y	T_PK_EP_SUM
PK_EP_SUM_ACT	T	Summary of PK endpoints of ACT-333679 by dose level and treatment	PKS	Y	T_PK_EP_SUM
PK_SUM_RATIO	T	Summary of PK parameters of ratio ACT-333679/selexipag concentration by dose level and treatment	PKS		T_PK_RATIO_SUM
PK_MM_SEL	T	Mixed model analysis: Ratio of Uptravi and i.v. selexipag period for selexipag by dose level	PKS	Y	T_PK_MM
PK_MM_ACT	T	Mixed model analysis: Ratio of Uptravi and i.v. selexipag period for ACT-333679 by dose level	PKS	Y	T_PK_MM
PK_POW_AUC_SEL	T	Dose proportionality of AUCtau of selexipag after i.v. selexipag: Power model estimation	PKS	Y	T_PK_POW
PK_POW_AUC_SEL	F	Dose proportionality of AUCtau of selexipag after i.v. selexipag: Power model estimation	PKS	Y	F_PK_POW
PK_POW_AUC_ACT	T	Dose proportionality of AUCtau of ACT-333679 after i.v. selexipag: Power model estimation	PKS	Y	T_PK_POW
PK_POW_AUC_ACT	F	Dose proportionality of AUCtau of ACT-333679 after i.v. selexipag: Power model estimation	PKS	Y	F_PK_POW
PK_WIL_SEL	T	Location shift analysis of tmax, ss of selexipag	PKS		T_PK_WIL
PK_WIL_ACT	T	Location shift analysis of tmax, ss of ACT-333679	PKS		T_PK_WIL

* T=Summary table, L=Listing, F=Figure, **SCR=Screened analysis set, SAF=Safety analysis set, ivSAF=i.v. Safety analysis set, PKS=Pharmacokinetic analysis set

12.9 Subject listings

Output name	Display*	Title (Description)	Analysis set(s)**	Key deliverable	Mock layout
SCRF	L	Listing of screening failures	SCR		L_SCRF
PWDS	L	Listing of reasons for premature discontinuation from the study	SAF		L_PWDS
PD	L	Listing of protocol deviations	SCR		L_PD
ANSET	L	Listing of analysis sets	SCR		L_ANSET
PWDT	L	Listing of reasons for premature discontinuation of i.v. selexipag treatment	ivSAF		L_PWDT
DEM	L	Listing of demographics	SCR		L_DEM
BAS	L	Listing of baseline disease characteristics	SCR		L_BAS
MH	L	Listing of medical history	SAF		L_MH
CM	L	Listing of previous and concomitant therapies	SAF		L_CM
CM_PAH_MOD	L	Listing of PAH specific therapies newly started dose changed or stopped during any period. [Add footnote: Interruptions of Utravi during i.v. selexipag period as mandated in the protocol are not shown.]	SAF		L_CM
EXP_PO	L	Listing of Utravi dosing records	SAF		L_EXP_PO
EXP_IV	L	Listing of study treatment dosing records	ivSAF		L_EXP_IV
COMP	L	Listing of compliance	ivSAF		L_COMP
AE	L	Listing of all adverse events	SCR		L_AE
AE_SCR	L	Adverse events in the Screening Period prior to the first dose of Utravi on Visit 2 Day 1	SCR		L_AE
AE_DTH	L	Listing of all adverse events leading to death	SAF		L_AE
SAE	L	Listing of all serious adverse events	SAF		L_AE

Output name	Display*	Title (Description)	Analysis set(s)**	Key deliverable	Mock layout
AE_PC	L	Listing of all prostacyclin-associated adverse events	SAF		L_AE
AE_RMP	L	Listing of all adverse events of special interest based on the Utravi risk management plan [Replace SOC with Risk category in the Shell. Delete SOC on footnote regarding MedDRA version.]	SAF		L_AE
AE_INJDET	L	Listing of all injection site reactions	ivSAF		L_AEINJ
AE_PAH	L	Listing of PAH related adverse events	SAF		L_AE
AE_DC	L	Listing of adverse events leading to discontinuation of study treatment	ivSAF		L_AE
AE_REL	L	Listing of adverse events related to study treatment as judged by the investigator	ivSAF		L_AE
LAB	L	Listing of laboratory parameters	SCR		L_LAB
VS	L	Listing of vital signs, body weight and height	SCR		L_VS
EG	L	Listing of quantitative ECG measurements	SAF		L_EG
EG_QUAL	L	Listing of qualitative ECG findings	SAF		L_EG_QUAL
WHO	L	Listing of WHO functional class	SCR		L_WHO
PK_CONC	L	Listing of selexipag / ACT-333679 plasma concentrations	PKS		L_PK_CONC
PK_DER	L	Listing of derived PK parameters of selexipag and ACT-333679	PKS		L_PK_DER
PK_RATIO	L	Listing of Cmax,ss and AUCtau,ss ratio of ACT-333679/selexipag	PKS		L_PK_RATIO
IMP_CONC	L	Listing of selexipag concentration in the infusion solution	PKS		L_IMP_CONC

* T=Summary table, L=Listing, F=Figure, **SCR=Screened analysis set, SAF=Safety analysis set, ivSAF=i.v. Safety analysis set, PKS=Pharmacokinetic analysis set

14 APPENDICES

Appendix A Protocol synopsis

PROTOCOL SYNOPSIS AC-065A309

TITLE	A multicenter, open-label, single-sequence cross-over study to assess safety, tolerability, and pharmacokinetics of intravenous selexipag in subjects with stable pulmonary arterial hypertension switching from an oral stable dose of selexipag
OBJECTIVES	
Primary objective(s)
 
The primary objective of this study is to assess whether temporary switching from a stable oral dose of selexipag to an intravenous (i.v.) dose of selexipag providing comparable exposure to active metabolite ACT-333679 and switching back to the initial oral dose of selexipag is safe and well tolerated in subjects with stable pulmonary arterial hypertension (PAH).
 
Other objectives
 
Other objectives are described in Section 2.2.

DESIGN	
This is a prospective, multi-center, open-label, single-sequence, cross-over, Phase 3 study.
 
Subjects with stable PAH, currently treated with Uptravi® at a stable dose (i.e., unchanged dose for 28 days), will be enrolled.
 
Subjects will be hospitalized during Period 1 (pre-treatment period) and Period 2 (treatment period).
 
No interim analysis is planned.

PERIODS	
Screening period:
 
Up to 28 days; starts with the signing of the Informed Consent Form (ICF) and ends with first day (Visit 2, Day 1) of Period 1 (Uptravi, pre-treatment period).
 
Treatment and observation period:
 
The treatment and observation period includes the following consecutive periods:
 
• Period 1 (Uptravi, pre-treatment period, in-hospital): 1 day Starts with intake of the morning dose of Uptravi at Visit 2 Day 1 and ends the following day, before initiation of the first infusion of i.v. selexipag.• Period 2 (i.v. selexipag, treatment period, in-hospital): 36 hours (3 doses) Starts in the morning of Visit 2 on Day 2 with the start of the

	
first infusion of i.v. selexipag and ends in the evening of Visit 2 on Day 3 before the evening administration of Uptravi. Note: oral administration of Uptravi is interrupted during the treatment period with i.v. selexipag.
 
• Period 3 (Uptravi, post-treatment period): 7 to 11 days Starts in the evening of Visit 2 on Day 3 with the oral administration of Uptravi and ends 7 to 11 days later, at Visit 3. 
Safety Follow-up period: Starts at the end of Visit 3 and ends 30 to 37 days after the last administration of i.v. selexipag with the End-of-Study telephone call (Visit 4).

PLANNED DURATION	Approximately 9–12 months from first subject first visit to last subject last visit.
SITE(S) / COUNTRY(IES)	10 sites in 2 countries (planned).
SUBJECTS / GROUPS	
Approximately 20 subjects will be enrolled in order to obtain 18 evaluable subjects.
 
Two different groups of subjects will be enrolled based on their dose of Uptravi:
 
- Group A: Subjects with a stable dose of Uptravi between 200 and 1000 µg twice daily (b.i.d.; inclusive): at least 5 and up to 8 subjects will be enrolled in this dose group.- Group B: Subjects with a stable dose of Uptravi between 1200 and 1600 µg b.i.d. (inclusive): At least 12 and up to 15 subjects will be enrolled in this dose group.
INCLUSION CRITERIA	
1. Signed ICF prior to any study-mandated procedure.2. Male and female subjects at least 18 to 75 years inclusive.3. Subjects with PAH belonging to the Updated Clinical Classification Group 1 [Galiè 2016]4. Subjects who have been prescribed Uptravi in compliance with local prescribing information (i.e., SmPC or USPI).5. Stable PAH defined as WHO Functional Class (FC) I–III at Visit 1 and Visit 2 and no change (i.e., introduction or dose change) in PAH-specific medication (i.e., ERA, PDE-5 inhibitor or sGC stimulator) and diuretics in the last 28 days prior to Visit 2.6. Subjects currently treated with Uptravi at a stable dose (i.e., unchanged dose) for at least 28 days before Visit 2.7. A woman of childbearing potential is eligible only if she has a negative urine pregnancy test at Visit 1 and at Visit 2.
EXCLUSION	
1. Pregnant, planning to become pregnant or lactating.

CRITERIA	
2. Known and documented moderate or severe hepatic impairment.3. Subjects having received gemfibrozil at any time since initiation of Uptravi.4. Treatment with any prostacyclin and prostacyclin analogs within 28 days prior to Visit 1.5. SBP < 90 mmHg at Visit 1 or at Visit 2.6. Known or suspected uncontrolled hyperthyroidism.7. Severe renal failure and ongoing or planned dialysis.8. Any known factor or disease that might interfere with treatment compliance, study conduct, or interpretation of the results, such as drug or alcohol dependence or psychiatric disease.9. Known concomitant life-threatening disease with a life expectancy < 12 months.10. Treatment with another investigational treatment within 3 months of Visit 1.
STUDY TREATMENTS	
Investigational treatment
 
The study treatment (i.v. selexipag) will be administered b.i.d. intravenously as an infusion over an 87 minute period [see Section 5.1.4]. The dose of i.v. selexipag will be individualized for each subject and will aim to reach an exposure to the active metabolite (area under the concentration-time curve [AUC] between two doses) comparable to the one obtained with subject's current oral dose of Uptravi.
 
Comparator and/or placebo
 
Not applicable.

AUXILIARY MEDICINAL PRODUCTS	The study population consists of subjects who have been prescribed Uptravi (oral selexipag) as part of their standard PAH treatment (i.e., Uptravi must not have been prescribed solely for the purpose of the study). Subjects will keep using Uptravi during their participation in the study as prescribed by their physician and in compliance with the USPI/SmPC [Uptravi® SmPC; Uptravi® USPI] including the use of contraception for women of childbearing potential. Subject's oral treatment with Uptravi will be temporarily interrupted for 36 hours during the administration of study treatment (i.v. selexipag).
ENDPOINTS	
Primary efficacy endpoint(s)
 
Not applicable.
 
Secondary efficacy endpoints
 
Not applicable.

	
Main safety and tolerability endpoints
 
The main safety and tolerability endpoints will be analyzed over the Period 1, Period 2, and Period 3 combined.
 
- Discontinuations due to prostacyclin-associated adverse events (AEs).- AEs and serious AEs (SAEs).- Prostacyclin-associated AEs.- AEs related to injection site reactions.- PAH-related AEs. 
Other endpoints
 
Other endpoints are described in Section 6.2.3.

PHARMACOKINETIC ENDPOINTS	
- The AUC during a dose interval at steady state ($AUC_{t, ss}$) of selexipag and its active metabolite, ACT-333679, at steady state after Uptravi (oral selexipag) in Period 1 and after i.v. selexipag administration in Period 2.- The maximum plasma concentration at steady state ($C_{max, ss}$) of selexipag and its active metabolite, ACT-333679 after Uptravi (oral selexipag) in Period 1 and i.v. selexipag administration in Period 2.- The time to reach maximum plasma concentration at steady-state ($t_{max, ss}$) of selexipag and its active metabolite, ACT-333679 after Uptravi (oral selexipag) in Period 1 and i.v. selexipag administration in Period 2.- Trough plasma concentration at steady state ($C_{trough, ss}$) of selexipag and its active metabolite, ACT-333679 after Uptravi (oral selexipag) in Period 1 and i.v. selexipag administration in Period 2.
ASSESSMENTS	Refer to the schedule of assessments in Table 2.
STATISTICAL METHODOLOGY	
Approximately 20 patients will be enrolled. In the GRIPHON Phase 3 pivotal study of selexipag, a proportion of 7.5% of patients on selexipag prematurely discontinued the study (i.e., without a morbidity/mortality event) due to prostacyclin-associated AEs. It is expected that the proportion of discontinuations will not be higher than 10%.
 
The statistical analysis will be mainly descriptive, i.e., no hypotheses will be formally tested.
 
Four analysis sets are defined in this study:
 
- Screened Analysis Set includes all subjects who are screened and have a subject identification number.

	
- i.v. Safety Set comprises all subjects who received at least one dose of i.v. study treatment.- Safety Set (SAF) includes all enrolled (included in the study on Day 1) subjects who receive at least one dose of selexipag (oral or i.v.).- Pharmacokinetic Analysis Set (PKS) comprises all subjects included in the SAF who received the 3 doses of i.v. study treatment and who complied with the protocol sufficiently and did not deviate from the protocol in a way that might affect the PK outcome of the study. 
The study comprises 3 main periods for analysis: Period 1, Period 2, and Period 3 and follow-up. AEs and SAEs will be tabulated, for the Safety Set and i.v. Safety Set, overall across periods as well as by study period. The proportion of discontinuations due to prostacyclin-associated AEs will be tabulated for the i.v. Safety Set and the SAF to address the primary objective. Due to the sample size, the proportion will be provided with a conservative 95% Clopper-Pearson confidence interval based on exact methods.
 
All secondary safety endpoints will be listed and tabulated in Safety Set and i.v. Safety Set.
 
Exposure will be summarized.
 
ECG abnormalities and laboratory variables will be descriptively summarized, both longitudinally across the study periods as well as separately per period. Death will be summarized by cause, by period, and overall.
 
The proportion of patients in each WHO FC (I, II, III and IV) will be tabulated at baseline and post-baseline, as well as the change in WHO FC at all assessed time points. Also the absence of worsening in WHO FC will be tabulated (i.e., patients that are either stable or improve).

--	---

Appendix B Visit and assessment schedule

PERIODS	Name	SCREENING	TREATMENT AND OBSERVATION PERIOD			FOLLOW-UP		
			Period 1 (Pre-treatment Period; Uptravi)	Period 2 (Treatment Period; i.v. selexipag)				
VISITS ¹	Number	Visit 1	Visit 2			Visit 3	Visit 4 (Phone call)	
	Name	Screening	Baseline				EOS	
	Time	Day -28 to Day -1	Day 1	Day 2 IV-1 (AM)	Day 2 IV-2 (PM)	Day 3 IV-3 (AM)	Day 12 (± 2days)	30 to 37 days after i.v. study treatment discontinuation
Informed consent		X						
Eligibility		X	X					
Demographics / Medical history		X						
WHO FC		X	X			X ²	X	
Previous/concomitant therapy		X	X	X	X	X	X	
Physical examination		X					X	
Vital signs (BP, pulse rate)		X	X	X ⁵		X ⁵	X	
Body weight and Height ³		X	X			X	X	
Hospitalization ^{4**}			<—————>					
Laboratory tests*		X	X ⁶			X	X	
12-lead ECG*			X	X ⁷	X ⁷	X ⁷	X	
Urine pregnancy test**		X	X				X	
PK sampling ⁸			X			X		
Study treatment administration (i.v. selexipag)				X	X	X		
Infusion solution sampling ⁹				X	X	X		
SAEs/AEs ¹⁰		X	X	X	X	X	X	

AE = adverse event; BP = blood pressure; ECG = electrocardiogram; EOS = End-of-Study; FC = Functional Class; i.v. = intravenous; PK = pharmacokinetic; SAE = serious adverse event; WHO = World Health Organization. *Electronically transferred to sponsor. ** Assessment not collected in CRF

- 1 Unscheduled visits may be performed at any time during the study. Assessments performed during unscheduled visits are at the discretion of the investigator.
- 2 On Day 3, WHO FC is to be assessed at the end of the i.v. selexipag infusion.
- 3 Height will be assessed at Visit 1 (screening) only.
- 4 In-patient hospitalization of subjects is mandatory during Visit 2 (Period 1 and Period 2) (i.e., 2 overnight stays from Day 1 to Day 3). For convenience, the hospitalization may be extended to the night before Day 1 and to the night of Day 3.
- 5 Vital signs (BP and pulse rate) will be assessed at 7 different time points.
- 6 If Visit 1 and Visit 2 Day 1 are performed within 7 days, laboratory tests and physical examination do not have to be repeated at Visit 2 Day 1.
- 7 ECG will be performed at pre-dose and within 30 minutes after stopping of infusion (i.v. selexipag).
- 8 PK profile includes 7 blood samples.
- 9 Infusion solution samples will be taken from the tubing before each infusion.
- 10 All AEs and SAEs that occur after signing the Informed Consent Form and up to 30 days after i.v. selexipag study treatment discontinuation must be reported.

Appendix C Discussion and further considerations of the applied statistical methods

Not applicable.

Appendix D Definitions of marked abnormalities and elevated liver function tests

Table 14 Thresholds for marked laboratory abnormalities

Laboratory test name	LL	LLL	HH	HHH
Hemoglobin (g/L)	< 100	< 80	Increase of > 20 g/L above baseline	Increase of > 40 g/L above baseline
Hematocrit (L/L)	< 0.28 (female) < 0.32 (male)	< 0.20	> 0.55 (female) 0.60 (male)	> 0.65
Platelet count (10E9/L)	< 75	< 50	> 600	> 999
Leukocytes (10E9/L)	< 3.0	< 2.0	> 20.0	> 100.0
Neutrophils (10E9/L)	< 1.5	< 1.0	NA	NA
Eosinophils (10E9/L)	NA	NA	> 5.0	NA
Lymphocytes (10E9/L)	< 0.8	< 0.5	> 4.0	> 20
ALT (U/L)	NA	NA	> 3 × ULN	> 5 × ULN
AST (U/L)	NA	NA	> 3 × ULN	> 5 × ULN
Alkaline phosphatase (U/L)	NA	NA	> 2.5 × ULN	> 5 × ULN
Total bilirubin (μmol/L)	NA	NA	> 2 × ULN	> 5 × ULN
Creatinine (μmol/L)	NA	NA	> 1.5 × ULN	> 3 × ULN
Sodium (mmol/L)	NA	< 130	> 150	> 155
Potassium (mmol/L)	< 3.2	< 3.0	> 5.5	> 6.0

ALT = alanine aminotransferase; AST = aspartate aminotransferase; NA = not applicable; SI = international system of units; ULN = upper limit of normal.

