14 APPENDICES

Appendix 1 Marked laboratory abnormalities

Laboratory values below or above the normal range will be graded at three levels (H, HH, HHH for values above normal range and L, LL, LLL for values below the normal range) where L stands for “low”, H for “high”.

The term “marked abnormality” describes laboratory values, with grading of abnormalities at two levels: LL/HH and LLL/HHH. These thresholds have been defined by the sponsor for the purpose of standardized data analysis and reporting by the sponsor. The definitions of marked abnormal values are based mainly on the CTCAE grading system [\[CTCAE 2010\]](#) [see Table 5].

The marked abnormal values (i.e., LL, LLL, HH, HHH) will also be used as flags and alerts on the laboratory reports to the investigators, and Actelion:

- Marked abnormality HH/LL: flag on laboratory report to investigators.
- Extreme marked abnormality HHH/LLL: alert on laboratory report to investigators and subject to additional communication to investigator via telephone call and to Actelion via email.

Thresholds for abnormality of level L or H are not provided in this appendix but will be provided in the central laboratory manual. Variables for which no threshold is defined in the table below may be defined in the central laboratory manual.

Table 5 **Thresholds for marked laboratory abnormalities**

Laboratory test name (SI unit)	LL	LLL	HH	HHH
Hemoglobin (g/L)	< 100	< 80	Increase of > 20 g/L above ULN or above baseline (if baseline > ULN)	Increase of > 40 g/L above ULN or above baseline (if baseline > ULN)
Hematocrit (L/L)	< 0.28 (female) < 0.32 (male)	< 0.20	> 0.55 (female) > 0.60 (male)	> 0.65
Platelet count (10^9 /L)	< 75	< 50	> 600	> 999
Leukocytes (10^9 /L)	< 3.0	< 2.0	> 20.0	> 100.0
Neutrophils (10^9 /L)	< 1.5	< 1.0	NA	NA
Eosinophils (10^9 /L)	NA	NA	> 5.0	NA
Lymphocytes (10^9 /L)	< 0.8	< 0.5	> 4.0	> 20
ALT (U/L)	NA	NA	> 3 \times ULN	> 5 \times ULN
AST (U/L)	NA	NA	> 3 \times ULN	> 5 \times ULN
Alkaline phosphatase (U/L)	NA	NA	> 2.5 \times ULN	> 5 \times ULN
Total bilirubin (μ mol/L)	NA	NA	> 2 \times ULN	> 5 \times ULN
Creatinine (μ mol/L)	NA	NA	> 1.5 \times ULN	> 3 \times ULN
Sodium (mmol/L)	NA	< 130	> 150	> 155
Potassium (mmol/L)	< 3.2	< 3.0	> 5.5	> 6.0

ALT = alanine aminotransferase; AST = aspartate aminotransferase; NA = not applicable; SI = international system of units; ULN = upper limit of normal.

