7.4.3 Analysis

All laboratory values will be listed. Values from local laboratories will be flagged in data listings and not used in any analysis.

7.4.3.1 *Values over time*

For continuous laboratory variables, descriptive statistics will be provided for observed values as well as for change from baseline at each scheduled study visit.

7.4.3.2 *Individual subject changes*

Laboratory test results from both, scheduled and unscheduled visits will be used to determine the incidence of markedly abnormal test results. The date of the sample will determine the analysis period the test is assigned to.

The number of subjects with newly occurring or worsening markedly abnormal laboratory values will be displayed for the analysis sets shown in [Table 4](#) and the periods shown in [Table 7](#).

The definitions of marked abnormal lab values are shown in [Appendix D](#).

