Programming note: Continue for all Hematology/Clinical chemistry parameters as stated in Section 7.4 of the SAP.

T_LB_ABN

ACT-293987

Protocol: AC-065A309

Incidence of marked laboratory values, by period

Analysis Set: Safety Analysis Set

Period 2: i.v. selexipag, treatment period

Category Parameter	Grade	Severity of abnormality	Uptravi b.i.d. dose		
			200-1000 ug N = xxx n / m (%)	1200-1600 ug N = xxx n / m (%)	Total N = xxx n / m (%)
Hematology					
Hemoglobin	LL	< 100 g/L	xxx / xxx (xx.x)	xxx / xxx (xx.x)	xxx / xxx (xx.x)
	LLL	< 80 g/L	xxx / xxx (xx.x)	xxx / xxx (xx.x)	xxx / xxx (xx.x)
	HH	Increase > 20 g/L above baseline	xxx / xxx (xx.x)	xxx / xxx (xx.x)	xxx / xxx (xx.x)
	HHH	Increase > 40 g/L above baseline	xxx / xxx (xx.x)	xxx / xxx (xx.x)	xxx / xxx (xx.x)
Hematocrit	LL	< 0.28 L/L [f], < 0.32 L/L [m]	xxx / xxx (xx.x)	xxx / xxx (xx.x)	xxx / xxx (xx.x)
	LLL	< 0.2 L/L	xxx / xxx (xx.x)	xxx / xxx (xx.x)	xxx / xxx (xx.x)
	HH	> 0.55 L/L [f], > 0.60 L/L [m]	xxx / xxx (xx.x)	xxx / xxx (xx.x)	xxx / xxx (xx.x)
	HHH	> 0.65 L/L	xxx / xxx (xx.x)	xxx / xxx (xx.x)	xxx / xxx (xx.x)
Platelet count	LL	< 75 x10^9/L	xxx / xxx (xx.x)	xxx / xxx (xx.x)	xxx / xxx (xx.x)
	LLL	< 50 x10^9/L	xxx / xxx (xx.x)	xxx / xxx (xx.x)	xxx / xxx (xx.x)
	HH	> 600 x10^9/L	xxx / xxx (xx.x)	xxx / xxx (xx.x)	xxx / xxx (xx.x)
	HHH	> 999 x10^9/L	xxx / xxx (xx.x)	xxx / xxx (xx.x)	xxx / xxx (xx.x)
Leukocytes	LL	< 3.0 x10^9/L	xxx / xxx (xx.x)	xxx / xxx (xx.x)	xxx / xxx (xx.x)
	LLL	< 2.0 x10^9/L	xxx / xxx (xx.x)	xxx / xxx (xx.x)	xxx / xxx (xx.x)
	HH	> 20.0 x10^9/L	xxx / xxx (xx.x)	xxx / xxx (xx.x)	xxx / xxx (xx.x)
	HHH	> 100.0 x10^9/L	xxx / xxx (xx.x)	xxx / xxx (xx.x)	xxx / xxx (xx.x)
Neutrophils	LL	< 1.5 x10^9/L	xxx / xxx (xx.x)	xxx / xxx (xx.x)	xxx / xxx (xx.x)
	LLL	< 1.0 x10^9/L	xxx / xxx (xx.x)	xxx / xxx (xx.x)	xxx / xxx (xx.x)
Eosinophils	HH	> 5.0 x10^9/L	xxx / xxx (xx.x)	xxx / xxx (xx.x)	xxx / xxx (xx.x)
Lymphocytes	LL	< 0.8 x10^9/L	xxx / xxx (xx.x)	xxx / xxx (xx.x)	xxx / xxx (xx.x)
	LLL	< 0.5 x10^9/L	xxx / xxx (xx.x)	xxx / xxx (xx.x)	xxx / xxx (xx.x)
	HH	> 4.0 x10^9/L	xxx / xxx (xx.x)	xxx / xxx (xx.x)	xxx / xxx (xx.x)

	HHH	> 20.0 x10^9/L	xxx / xxx (xx.x)	xxx / xxx (xx.x)	xxx / xxx (xx.x)
Biochemistry					
ALT	HH	> 3 xULN	xxx / xxx (xx.x)	xxx / xxx (xx.x)	xxx / xxx (xx.x)
	HHH	> 5 xULN	xxx / xxx (xx.x)	xxx / xxx (xx.x)	xxx / xxx (xx.x)
AST					
	HH	> 3 xULN	xxx / xxx (xx.x)	xxx / xxx (xx.x)	xxx / xxx (xx.x)
	HHH	> 5 xULN	xxx / xxx (xx.x)	xxx / xxx (xx.x)	xxx / xxx (xx.x)

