Alkaline phosphatase					
	HH	> 2.5 xULN	xxx / xxx (xx.x)	xxx / xxx (xx.x)	xxx / xxx (xx.x)
	HHH	> 5 xULN	xxx / xxx (xx.x)	xxx / xxx (xx.x)	xxx / xxx (xx.x)
Total bilirubin					
	HH	> 2 xULN	xxx / xxx (xx.x)	xxx / xxx (xx.x)	xxx / xxx (xx.x)
	HHH	> 5 xULN	xxx / xxx (xx.x)	xxx / xxx (xx.x)	xxx / xxx (xx.x)
Creatinine					
	HH	> 1.5 xULN	xxx / xxx (xx.x)	xxx / xxx (xx.x)	xxx / xxx (xx.x)
	HHH	> 3 xULN	xxx / xxx (xx.x)	xxx / xxx (xx.x)	xxx / xxx (xx.x)
Sodium					
	LLL	< 130 mmol/L	xxx / xxx (xx.x)	xxx / xxx (xx.x)	xxx / xxx (xx.x)
	HH	> 150 mmol/L	xxx / xxx (xx.x)	xxx / xxx (xx.x)	xxx / xxx (xx.x)
	HHH	> 155 mmol/L	xxx / xxx (xx.x)	xxx / xxx (xx.x)	xxx / xxx (xx.x)
Potassium					
	LL	< 3.2 mmol/L	xxx / xxx (xx.x)	xxx / xxx (xx.x)	xxx / xxx (xx.x)
	LLL	< 3.0 mmol/L	xxx / xxx (xx.x)	xxx / xxx (xx.x)	xxx / xxx (xx.x)
	HH	> 5.5 mmol/L	xxx / xxx (xx.x)	xxx / xxx (xx.x)	xxx / xxx (xx.x)
	HHH	> 6.0 mmol/L	xxx / xxx (xx.x)	xxx / xxx (xx.x)	xxx / xxx (xx.x)

ULN = Upper limit of normal. Subjects are summarized in each category they fall into.

n = Subjects with event, m = Subjects with assessment in the specified time period (at risk)

Post-baseline abnormalities not present at baseline or abnormalities worsening after baseline are shown.

Output: <Output name>, Produced by DATAMAP on ddMMMyyyy hh:mm (CET),

SDTM Date: ddMMMyyyy

Program: /<folder>/<program_name>.sas

Page x of y

Programming note: Use the following labels:

Analysis Period	Label in summary table
1	Period 1: Uptravi, pre-treatment period
2	Period 2: i.v. selexipag, treatment period
3&FU	Period 3: Uptravi, post-treatment period including safety follow-up period
2&3&FU	Period 2 & 3: i.v. selexipag, treatment period and Uptravi, post-treatment period including safety follow-up period combined

T_VS_SUM

ACT-293987

Protocol: AC-065A309

Summary and change from baseline of vital signs, by visit

Analysis Set: Safety Analysis Set

Parameter: Systolic blood pressure [mmHg]

Treatment group Time point	n	Baseline				Time Point				Change from baseline						
		Mean	SD	Median	Min	Max	Mean	SD	Median	Min	Max	Mean	SD	Median	Min	Max
Uptravi b.i.d. dose 200-1000 ug (N=xxx)																
Baseline	xx	xxxx.x	xx.xx	xxxx.x	xxx	xxx										
Visit 2 Day 2 + 0 h	xx	xxxx.x	xx.xx	xxxx.x	xxx	xxx	xxxx.x	xx.xx	xxxx.x	xxx	xxx	xxxx.x	xx.xx	xxxx.x	xxx	xxx
+25 min	xx	xxxx.x	xx.xx	xxxx.x	xxx	xxx	xxxx.x	xx.xx	xxxx.x	xxx	xxx	xxxx.x	xx.xx	xxxx.x	xxx	xxx

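### The SAP grades hemoglobin HH/HHH on rise from baseline alone, dropping the protocol's ULN condition, so values within or below the normal range can be tabulated as marked high

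*SAP*

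**What the plan says.** Protocol Appendix 1, Table 5, gives hemoglobin HH as "Increase of > 20 g/L above ULN or above baseline (if baseline > ULN") and HHH as "Increase of > 40 g/L above ULN or above baseline (if baseline > ULN"). The text above that table reserves the high grades: "H, HH, HHH for values above normal range". It also says the thresholds were set for the sponsor's analysis and reporting, as well as for flags and alerts on the laboratory reports.

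SAP Appendix D, Table 14, gives HH as "Increase of > 20 g/L above baseline" and HHH as "Increase of > 40 g/L above baseline". ULN does not appear in either hemoglobin cell. Shell T_LB_ABN in SAP Appendix E carries the rule into the output with the row label "Increase > 20 g/L above baseline", and a matching row for 40 g/L.

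SAP Section 7.4.3.2 makes Appendix D the operative source for the counts: "The definitions of marked abnormal lab values are shown in" that appendix. The numeric cut-offs for the other laboratory tests agree between the two documents.

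SAP Section 11.1 reports no changes to the protocol's analyses. Section 11.3 and the document history do not mention hemoglobin thresholds.

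**The concern.** Marked laboratory abnormalities are a protocol endpoint (Protocol Section 6.2.3), and their proportion is a listed safety variable (Section 10.2.3). The two documents define one of them differently, and the SAP does not say so.

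The difference goes to the meaning of the grade. In the protocol a high grade says that the value is above the normal range. Under the SAP rule the same label can attach to a subject whose hemoglobin has risen from a low baseline to a normal, or still low, value. The published table would then show a marked or extreme high abnormality where the protocol's definition finds none.

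There is also a traceability problem. Under Protocol Section 7.2.4.1 and Appendix 1, the central laboratory's flags and alerts follow the protocol thresholds. The HH/HHH flags in the study tables and in listing L_LAB are derived separately under the SAP. The same sample may therefore be unflagged on the site report and HH or HHH in the study report.

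**Working it through.** **Inputs.** Rise limits k = 20 g/L (HH) and 40 g/L (HHH), from both tables. Marked-low cut (LL) of 100 g/L, the same in both. The documents give no hemoglobin ULN, so I assume a range of 150 to 180 g/L. Write b for baseline, v for the later value and u for ULN.

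**Rules.**
- Protocol: flag if v > max(b, u) + k.
- SAP: flag if v > b + k.

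**Where they differ.**
- If b ≥ u, then max(b, u) = b and the rules are identical.
- If b < u, the SAP alone flags values with b + k < v ≤ u + k. This band is u − b wide. For b = 110 it is 150 − 110 = 40 to 180 − 110 = 70 g/L wide.
- Part of the band lies at or below ULN when b + k < u.

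**Direction.** Since max(b, u) ≥ b, every protocol flag is also a SAP flag. An integer grid (baseline 80 to 200, later value 80 to 240, six assumed ULNs from 150 to 180) confirmed this, with no pair flagged by the protocol alone.

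**Examples.**

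| Baseline to later value (g/L) | Rise | SAP grade | Protocol HH cut, u = 150 / u = 180 | Protocol marked-high grade |
|---|---|---|---|---|
| 78 to 99 | 21 | HH | > 170 / > 200 | none / none |
| 110 to 131 | 21 | HH | > 170 / > 200 | none / none |
| 95 to 136 | 41 | HHH | > 170 / > 200 | none / none |
| 165 to 186 | 21 | HH | > 185 / > 200 | HH / none |

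The first row barely depends on the assumed ULN. Any ULN at or above the LL cut of 100 puts the protocol HH cut at 120 or higher, while 99 still meets LL. The last row shows the rules agreeing once baseline exceeds ULN (u = 150) and parting again when it does not (u = 180).

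**Does the shell's filter help?** Its footnote reads "Post-baseline abnormalities not present at baseline or abnormalities worsening after baseline are shown". A post-baseline rise of more than 20 g/L is by construction not present at baseline, so the filter removes none of these cases. In the first row it would tend to suppress the LL count, because 78 was already below 100, and leave only HH.

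**Size of one extra flag.** 1/18 = 5.6 percentage points in the total. Safety tables are also split by dose cohort (SAP Section 7.7). In Group A, with 5 to 8 planned subjects, it is 1/8 = 12.5 to 1/5 = 20 points. These assume that every subject has an assessment, since the shell's denominator counts assessed subjects. The shell places subjects in every category they meet, so an HHH case adds to both rows.

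**The case against.** The best defence is that the SAP wording may be deliberate. SAP Table 1 lists a sponsor standard for marked laboratory abnormalities (OTH-000005, Version 9, 1 November 2017), which is later than the protocol of 27 January 2017. The baseline-only rule may come from there. Its content is not in the documents, so the SAP rule cannot be called a slip. A deliberate switch would still have to be declared in Section 11.1, and it would still conflict with what the protocol says the high grades mean.

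The output is also fairly transparent. The shell row states its criterion, and L_LAB prints each value beside its reference range, the laboratory's own H/L flag and the change from baseline. A careful reader could find an in-range HH. That softens the problem without correcting the count.

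The reach is small. The endpoint is in the protocol's other safety list, not the main one; the analysis is descriptive; SAP Section 12.7.10 does not mark the table as a key deliverable. The hemoglobin risk named in SAP Section 7.2.1.7 is a decrease, and the LL and LLL cuts are identical in both documents. Apart from unscheduled samples, post-baseline laboratory tests fall only on Day 3 and at Visit 3 (Day 12 ± 2), so rises of 21 or 41 g/L would have to develop quickly and may be rare. All of this stands, and it bears on priority.

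Four stronger readings are tempting and should be resisted:
- That the SAP counts every rise from baseline. It counts only rises above 20 or 40 g/L.
- That the protocol never uses baseline. It does when baseline exceeds ULN.
- That every extra flag is a false positive. Some would lie modestly above ULN, and they are excess only relative to the protocol's definition.
- That site flags and study tables will disagree. They may, if a subject falls in the band between the two cuts.

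**Conclusion.** The mismatch is real, undeclared and carried into the table shell. For subjects with baseline below ULN, the SAP rule can label values within or below the normal range as marked high, and it can only over-count relative to the protocol. The rule difference itself needs no assumption; the examples graded HH or HHH within the normal range rest on an assumed ULN of 150 to 180 g/L. How many subjects would be affected cannot be derived from the documents.

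The consequence is a possible inflation of two hemoglobin rows, by the amounts shown for each extra subject. A reader might infer that the trial's safety conclusion is at risk. The documents do not support that: the main safety endpoints, the sample size and the PK analysis do not use this rule. It should be corrected as a consistency item before the tables are produced.

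**What to change.** In SAP Table 14 and shell T_LB_ABN, define hemoglobin HH as a value more than 20 g/L above the higher of ULN and baseline, and HHH as more than 40 g/L above it. This is protocol Table 5 in one expression. Apply the same derivation to the flags in L_LAB.

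If the baseline-only rule is intended because the later sponsor standard requires it, declare and justify it in SAP Section 11.1, and report those rises under a separate label so that in-range values are not called HH or HHH.

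The cost is a wording change and one line of derivation. SAP Section 7.4.1 says the laboratory already supplies reference ranges with the results, and Section 7.4.2 already derives position against them. No new data are needed.
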